## 2.3 RISK/BENEFIT ASSESSMENT

### 2.3.1 KNOWN POTENTIAL RISKS

The Immediate risks include the risks associated with surgery such as pain, allergic reaction to the drugs used during surgery, bleeding and death. The possibility of a second surgery increases the previous risks.

The long-range risks include the following:

Because ScNS remodels the stellate ganglion and reduces sympathetic outflow, it is possible to slow down the sinus rate or atrioventricular (AV) conduction. If the following serious side effects are observed, the ScNS will be terminated:

- Third-degree AV block at any anatomic level associated with any one of the following conditions:
  - Bradycardia with symptoms presumed to be due to AV block.
  - Arrhythmias and other medical conditions that require drugs that result in symptomatic bradycardia.
  - Documented periods of asystole  $\geq 3.0$  seconds or any escape rate  $<40$  beats per minute (bpm) in awake, symptom-free patients.
- Second-degree AV block regardless of type or site of block, with associated symptomatic bradycardia

- Infection of the implanted devices
- Persistent pain at the lead site not responsive to drug therapy.
- Allergic response to the implanted lead or materials used
- Lead, extension or migration that results in loss of ability to perform ScNS

The following adverse events will be managed medically

- Skin irritation related to prolonged placement of 7-day Mobile Cardiac Telemetry patch.
- Pain, goosebumps, hot flashes, and other uncomfortable feelings related to electrical stimulation of the subcutaneous nerves.

Alternative methods of treating drug resistant symptomatic AF include catheter ablation procedures and open-heart surgery, both carry significant risks of morbidity and mortality.

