#### 6.1.2 DEVICE ENERGY AND ADMINISTRATION

The experimental group will receive stimulation ScNS at 3.5mA output, while the control group will receive no stimulation for 2 weeks.

The control group will have an option to crossover to the experimental group after three weeks from the first procedure and receive stimulation ScNS at 3.5 mA output.

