### 6.3 MEASURES TO MINIMIZE BIAS: RANDOMIZATION AND BLINDING

The patient will be consented to undergo surgery. After the device implantation, the patients will be randomized to experimental and control groups using Redcap. We will attempt to blind the patients, although the tingling or pain associated with the stimulation may make blinding difficult. All data analyses performed by the co-investigators and the rhythm analyses performed by the Mobile Cardiac Telemetry system technicians will be blinded. The experimental group will receive stimulation at 3.5 mA output, while the control group will receive no stimulation. Data will be obtained during this time to determine atrial arrhythmia frequencies in both groups. The device will then be removed at the end of the second week. After the third week, we will give the option to the control group to crossover to the experimental group. This group of patients will undergo a second procedure to receive stimulation at 3.5 mA and we will follow up for another 3 weeks and 3 months post second procedure.

We will tell the patients that they will be randomized into experimental group or control group during surgery. We will attempt to blind the patients, although the tingling or pain associated with the stimulation may make blinding difficult. We will explain to all patients they may or may not feel tingling and/or pain during the 2-week stimulation time but will not tell them which group they are assigned to. All data analyses performed by the co-investigators and the rhythm analyses performed by the 7-day non-invasive monitoring system technicians will be blinded. After 3 weeks post-procedure, we will unblind the control group to give them the option of crossing over to the experimental group to receive the treatment. If they agree, these group of patients will forego the 3-month follow-up visit and will proceed with a second procedure along with follow up visits post-second procedure. Data will be obtained during this time to determine AF burden in all groups.

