### 9.3 POPULATIONS FOR ANALYSES

1. Safety set: the set of patients who have undergone surgery to insert the subcutaneous lead
2. modified intention-to-treat set: the set of patients who have either the subcutaneous nerve stimulation or the sham stimulation performed AND have baseline average AF burden AND at least the first week's post-stimulation average AF burden.

Our sensitivity analysis on the modified intention-to-treat set will be using the safety set: we will assume 0 reduction in AF burden for patients missing either the baseline or the first week post-baseline AF burden.

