#### **Analysis of AF burden in patients crossed over from sham control to experimental group**

At the end of week three, patients in the sham control group will be given the option to receive the active treatment and treated the same way as patients on the treatment arm for weeks 1-3. Patient characteristics will be summarized for the subset of patients who accept this option to cross over to active treatment. The averages and SDs of AF burden will be computed for each week from baseline to week 6 for this group, and displayed graphically. Linear mixed models may be employed to explore the temporal changes in this subset of patients.

---

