#### **9.4.4 SAFETY ANALYSES**

- **Safety Endpoints**
  - Safety shall be evaluated throughout participation in the study:
  - Freedom of major implant adverse events related to the procedure
  - Infection
  - Lead, extension or migration
  - Persistent pain at the lead site
  - Freedom of Third Degree AV Block at any anatomic level associated with any one of the following conditions
  - Bradycardia with symptoms presumed to be due to AV Block
  - Arrhythmias and other medical conditions that require drugs that result in symptomatic bradycardia
  - Documented periods of asystole > 3.0 seconds or any escape rate <40 beats per minute in awake, symptom-free patients

- Freedom of Second-degree AV block regardless of type or site of block, with associated symptomatic bradycardia
- Freedom of skin irritation related to the ECG patches, Mobile Cardiac Telemetry patch
- Freedom of allergic response to the implanted lead or materials used

The number as well as percent of patients experiencing a safety outcome listed above will be summarized overall and by randomized group in the safety set.

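### Section 9.4.4 tabulates safety by randomized group over the whole of participation, so harms after a control's crossover implant and stimulation fall in the sham column

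*Combined protocol and SAP*

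**What the plan says.** Section 9.4.4 sets the time frame: "Safety shall be evaluated throughout participation in the study". It then lists the outcomes: major implant events, infection, lead migration, lead-site pain, AV block of defined kinds, skin irritation and allergy. The tabulation rule is that the number and "percent of patients experiencing a safety outcome listed above will be summarized overall and by randomized group in the safety set". Section 9.3 defines that set by surgery alone: "the set of patients who have undergone surgery to insert the subcutaneous lead".

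Section 6.1.2 adds the crossover: "The control group will have an option to crossover to the experimental group after three weeks from the first procedure". Section 6.3 says what it involves: "This group of patients will undergo a second procedure to receive stimulation at 3.5 mA", with follow-up to 3 weeks and 3 months after that procedure.

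The only analysis written for crossover patients is in section 9.4.3. It describes them as "given the option to receive the active treatment and treated the same way as patients on the treatment arm for weeks 1-3" and covers their characteristics and weekly AF burden. It does not cover safety.

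**The concern.** The sham arm allows harms of 3.5 mA stimulation to be told apart from harms of wearing a lead at 0 mA. Section 4.2 says stimulator output is the only difference between the groups. That holds until crossover. From then on, a control who accepts the option has had two implants and one active course, but is still tabulated as sham. The column that pools all patients does not separate this exposure either.

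The distortion differs by row. Where stimulation causes the harm, the two columns move together and the harm looks smaller than it is. Where the implant causes it, controls who cross over carry two implants against one in Group A, so sham can look the worse arm. Section 2.3.1 accepts the added hazard: "The possibility of a second surgery increases the previous risks". A reader of the final table could be misled in either direction.

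**Working it through.** **Inputs**

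- Group size: 15 per arm (section 9.2). It can be reproduced. The effect size is (76.3 − 5)/44.8 = 1.59. The normal approximation at two-sided 0.025 and 80% power gives 8 per arm. Dividing by 0.864, an assumed worst-case efficiency for the Wilcoxon test, gives 9.3, so 10. Then 10/0.70 = 14.3, so 15. The figure is not disputed; it is the denominator of each safety column.
- Infection risk per implant: p = 1/84 = 1.2% (section 8.1), taken as equal for first and second implants.
- Retention: 70% (section 9.2). 0.70 × 15 = 10.5, so 10 to 11 controls would be available to cross over if that loss has occurred by week 3.
- Number of controls crossing over, k: not in the documents, so a range is shown.
- Risk from one stimulation course, q: not in the documents. It cancels in step 2.

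**Step 1. Follow one event through the rules.** A control crosses over and develops symptomatic second-degree AV block during the active course. The patient had a lead inserted, so is in the safety set. The event falls within participation. The patient's randomized group is B. The event is therefore reported under sham.

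**Step 2. Harm from stimulation only, with no background risk under sham.** Expected patients are 15q in Group A and kq in Group B. The table shows a difference of (15 − k)q where the true difference is 15q, so it shrinks by k/15.

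**Step 3. Harm from the implant only.** Expected patients are 15p in Group A and (15 − k)p + k[1 − (1 − p)²] in Group B. At k = 8 and p = 1/84 this is 7 × 0.01190 + 8 × 0.02367 = 0.0833 + 0.1893 = 0.273, against 15/84 = 0.179. The true difference per implant is zero.

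| k | Step 2: shrinkage | Step 3: Group A | Step 3: Group B |
|---|---|---|---|
| 4 | 27% | 0.18 | 0.23 |
| 8 | 53% | 0.18 | 0.27 |
| 10 | 67% | 0.18 | 0.30 |
| 11 | 73% | 0.18 | 0.31 |

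**Step 4. Both sources together.** Take 1.2% per implant, an assumed 20% per stimulation course, and an assumed 50% uptake. Group A has 1 − 0.988 × 0.80 = 21.0%. The true sham risk is 1.2%, so the true difference is 19.8 points. The planned sham column would read 0.5 × 1.2% + 0.5 × [1 − 0.988 × 0.7904] = 0.6% + 11.0% = 11.6%. The displayed difference is 9.4 points, about half the true one.

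**The case against.** Several objections carry weight.

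- **The numbers are small.** At the only risk the documents supply, the distortion at k = 8 is 0.27 − 0.18 = 0.09 of a patient. No test or decision rule uses the table. This stands, and it limits how serious the point is. But with so few events, one or two in the wrong column can change how the table reads.
- **Uptake may be low.** The amendment history shows that the crossover came in with version 9, after patients had already been enrolled. Controls who had finished by then may not have been able to take it up. This also stands. The same entry says the option was added so that every participant has a chance of stimulation, so non-trivial uptake is plausible, but no rate is given.
- **k/15 assumes no sham background risk.** AV block may have one, since eligible patients can be on AV nodal blockers. That is fair, and k/15 is exact only without it. Step 4 shows that the shrinkage remains when the sham risk is above zero.
- **The DSMB sees the events, and a sensible analyst would split them.** Sections 8.3.5 and 10.1.6 describe oversight during the trial, not the final by-arm summary, and the charter is not available to check. Nothing in section 9 asks for a split, although a separate crossover analysis was written for AF burden.
- **Tabulating by randomized group is the usual intention-to-treat practice.** It is sound up to week 3, before crossover. After that it no longer describes what patients were exposed to.

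**Conclusion.** The point holds in a limited form. Followed as written, section 9.4.4 counts events after the second implant and 3.5 mA stimulation under sham. Stimulation harms would be understated by k/15 under the zero-background assumption: 27% to 53% for 4 to 8 crossovers, and up to about 67-73% if 70% retention applies by week 3. Implant harms could look worse under sham with no true difference. The direction follows from the text; the size depends on an unstated uptake and mostly unstated risks. The table is descriptive and the primary endpoint at week 1 is unaffected.

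Four stronger readings are not supported.

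- **Complete masking.** A reader might infer it at k = 15. That needs better retention than the plan assumes, if the 70% applies by week 3.
- **Much shorter follow-up under sham as planned.** That compares Group A with a sham-only period, which is not a column in the plan. Taking 3 months as 91 days plus 7 days of telemetry, Group A has about 98 days. A crossover control has 21 + 98 = 119 to 35 + 98 = 133 days, or more, because sections 1.2 and 8.1 allow a later second procedure after a repeat pre-operative visit.
- **A hidden proarrhythmic risk.** Section 4.3 places that effect at 0.5 mA in dogs, an output no patient receives. Section 6.3 does say "Data will be obtained during this time to determine atrial arrhythmia frequencies in both groups", but it closes by referring to AF burden, which section 9 analyzes. Telemetry also covers set weeks only. A tachyarrhythmia row is therefore a matter of preference.
- **Adverse events going unreported.** Section 9 sets out no general table of adverse events by arm, but sections 8.3.4 and 8.3.5 require recording and reporting. That is missing detail rather than an error.

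**What to change.** Change section 9.4.4 in two steps.

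1. Make the by-randomized-group comparison of the listed outcomes from first implant to the week-3 visit, cutting both groups there. This is the window all patients share before crossover.
2. For the whole of participation, assign each event by onset date and show each listed outcome in three columns: Group A; Group B before any second procedure (to the end of participation for those who do not cross over); and Group B from the second procedure onward. Give the number of patients and days at risk in each. The overall column can stay.

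The cost is wording and table layout. Section 8.3.4 already has time of onset recorded, so no visit, device, patient or test is added.

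The downsides should be stated with the table. Counts will be small and can only be described. Follow-up differs between the three columns, which is why days at risk and the week-3 comparison are needed. The third column holds self-selected controls who, under section 6.3, have been unblinded, so it is not a randomized comparison. Some late infection or pain in a crossover control will be hard to assign to the first or second site, since the sites may be only 1 to 2 cm apart.

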## 1.2 SCHEMA

\* Eligibility monitoring with mobile cardiac telemetry provided by Preventice will only serve as an option for potential patients that do not have any clinical ePatch monitoring completed in the past 6 months. Potential patients that have ePatch monitoring results with no change in medication since then, do not have to undergo mobile cardiac telemetry during Eligibility visit. \*\* Activities are to be repeated for control subjects only who choose to crossover to experimental group prior the second procedure. \*\*\*Second procedure is to be done within two weeks of the Week 3 Visit for crossover patients, if not, patient must complete another pre-op visit two weeks before the procedure. Pre-op visit will entail Labs (CBC, BMP), INR if patient is taking Coumadin, 12 Lead EKG and pre-op instructions.

All patients will have baseline cardiac rhythm monitoring using standard ECG patch electrodes. Cardiac rhythm monitoring will be done with clinically available 7-day non-invasive Mobile Cardiac Telemetry.

Among them, the 7-day non-invasive Mobile Cardiac Telemetry provided by Preventice will be performed during the two weeks of ScNS to ensure patient safety. The Bittium Faros monitor, a non-invasive patch electrode, will be applied at similar time points as Preventice Mobile Cardiac Telemetry device to monitor skin sympathetic nerve activity. Mobile cardiac telemetry will also be performed for a week after the end of stimulation and for a week at 3 months after surgery. An Apple watch will be used to detect AF episodes, if any, until the completion of the 3 Month Visit 7-day Mobile Cardiac Telemetry.

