## 4 STUDY DESIGN

### 4.1 OVERALL DESIGN

- *A statement of the hypothesis.*
  - To test the hypothesis that ScNS can be used to reduce the AF burden in patients with paroxysmal AF
- *Phase of the trial.*
  - Not applicable.
- *A description of the type/design of trial to be conducted (e.g., randomized, placebo-controlled, double-blinded, parallel design, open-label, dose escalation, dose-ranging, adaptive, cluster randomized, group sequential, multi-regional, superiority or non-inferiority design).*
  - This is a prospective randomized IDE study. The patients are randomized into Experimental and Control groups. There is an option for the Control group to crossover into the Experimental group after completion of obtaining the primary endpoint.
- *A description of methods to be used to minimize bias.*
  - The investigators are responsible for programming the device and cannot be blinded to the study. However, we will not tell the patients whether they are randomized into the experimental or the control group until the primary endpoint is complete. Technicians and physicians responsible for echocardiogram and ECG monitoring will be blinded.
- *The number of study groups/arms and study intervention duration.*
  - We will randomize the patients into:
    - Group A: Experimental group will undergo 3.5 mA ScNA for two weeks.
    - Group B: Sham control group will receive 0 mA stimulation for two weeks.

- *Indicate if single site or multi-site.*
  - This is a single site study.
- *Name of study intervention(s).*
  - Subcutaneous nerve stimulation (ScNS).

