#### 9.4.3 ANALYSIS OF THE SECONDARY ENDPOINT(S)

The analyses of the secondary endpoints will be performed on the modified ITT data set. Unless otherwise stated, two-tailed nominal p values will be reported.

##### Analysis of mean VR at the end of week 1

In dogs, ScNS reduces ventricular rate during AF. The mean VR was  $149 \pm 36$  bpm after the induction of AF. The VR significantly decreased to  $84 \pm 16$  bpm ( $p=0.011$ ) at the final week of ScNS. The same device that produces AF burden will also generate VR. First, we will summarize the proportion of patients who are AF-free at the end of week 1. Fisher's exact test will be performed to test if the proportions of AF-free patients are the same between the two treatment arms at a two-sided significance level of

0.025. Second, we will summarize the mean VRs using mean and standard deviation by time and by randomization group among the patients who experience AF.

We will classify patients into 3 groups based on the week 1 average VR: patients who do not experience AF as category 1, patients who experience AF with VR  $\leq$  110 bpm as category 2, and patients who experience AF with VR  $>$  110 bpm as category 3. Fisher's exact test will be performed to test if the distribution of the three categories are the same between the two treatment arms and the nominal p-value will be reported.

We will categorize average VR at other time points into three groups as described above, and analyze repeated average VR using ordinal repeated measure analysis with patient as the blocking variable, week and group as well as their interaction as independent variables. Proportional odds assumption will be checked.

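### Section 9.4.4 counts safety outcomes by randomized group with no cut-off at crossover, and its list has no item for sinus bradycardia

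*Combined protocol and SAP*

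**What the plan says.** Section 9.4.4 opens by stating that "Safety shall be evaluated throughout participation in the study". It then lists the safety outcomes and ends by saying that the number and "percent of patients experiencing a safety outcome listed above will be summarized overall and by randomized group", in the safety set. Section 9.3 defines that set as everyone who had the lead inserted, with no limit on time or exposure.

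The crossover analysis in section 9.4.3 says that, at the end of week three, "patients in the sham control group will be given the option to receive the active treatment". Sections 6.1.2 and 6.3 describe this as a second implant with 3.5 mA stimulation. Under section 6.3, control patients are unblinded at that point, and those who cross over are followed for a further 3 weeks and 3 months after the second procedure.

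On rhythm, section 2.3.1 says that, because stimulation reduces sympathetic outflow, "it is possible to slow down the sinus rate or atrioventricular (AV) conduction". Section 7.2 repeats that heart rate may fall. The rhythm outcomes in 9.4.4 are third-degree AV block with qualifying conditions, and second-degree AV block with symptomatic bradycardia. The only planned analysis of heart rate concerns AF: "we will summarize the mean VRs using mean and standard deviation by time and by randomization group among the patients who experience AF".

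**The concern.** Two features of the safety table do not fit the design.

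First, the columns are defined by randomization and the window is the whole of participation, but one arm may change exposure at week 3. From then on, the sham column can contain stimulated time and a second procedure. A by-arm difference caused by stimulation would be diluted, for every outcome on the list.

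Second, a slower sinus rate is an effect that the protocol itself predicts from the mechanism, yet no row would show it by arm. Rate-slowing drugs are part of the background: AV nodal blockers are among the prior therapies that qualify a patient under section 5.1, and nothing bars their continued use. Bradycardia can therefore occur in both arms, and an uncontrolled count cannot be attributed to stimulation. The sham comparison before crossover is what separates the two causes.

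**Working it through.** **Which events fall in which column.** Inputs: the window (9.4.4, all participation), the columns (9.4.4, randomized group), the population (9.3, all implanted patients) and the crossover (6.1.2, 6.3, 9.4.3). A control patient who crosses over is still in the safety set, still in the sham column and still under observation. An event during that patient's stimulation is a sham event under the written rule. No sentence in section 9 removes it.

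**Size of the dilution.** The documents give neither an event risk on stimulation nor an expected crossover share, so both are assumptions. Let p be the risk on stimulation, 0 the risk off it, and c the share of controls who cross over.

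- Active column: p. Sham column: c × p. Difference: p × (1 − c).
- p = 20%, 15 per arm: active 3.0 expected patients. Sham 0, 1.5 and 3.0 at c = 0%, 50% and 100%. Difference 20, 10 and 0 points.
- p = 10%: difference 10, 5 and 0 points. p = 30%: 30, 15 and 0 points.

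For any p, half the contrast is lost at 50% crossover and all of it at full crossover.

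**Procedure-related events.** Section 8.1 cites a trial-period infection rate of 1.2% (one of 84 patients). Take this as the risk per implant, independent between implants.

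- Active: 1.2%.
- Sham: (1 − c) × 0.012 + c × (1 − 0.988²), where 1 − 0.988² = 0.0239. This gives 1.8% at c = 50% and 2.4% at c = 100%.
- In patients: 15 × 0.012 = 0.18 against at most 15 × 0.0239 = 0.36. The effect is small, but it comes only from the number of implants.

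**Whether the list covers the sinus node.** The text of 9.4.4 prints three lines after third-degree AV block: symptomatic bradycardia presumed due to AV block, conditions needing drugs that cause symptomatic bradycardia, and asystole or a slow escape rate in awake, symptom-free patients. Sections 2.3.1 and 7.2 show the same three lines nested as conditions of third-degree AV block, and 9.4.4 keeps the lead-in that introduces them. Read that way, none concerns the sinus node. Read as separate outcomes, the drug line and the asystole line could catch some sinus events. The first still requires AV block, the second a drug, and the third the absence of symptoms. Symptomatic sinus bradycardia caused by stimulation is missed on either reading.

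**Other planned analyses.** Ventricular rate in 9.4.3 is summarized and categorized only for patients in AF. Section 8.3.4 records all adverse events, but section 9 plans no by-group summary of them.

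**The case against.** The strongest reply is that no data are lost and patients are protected. Section 5.2 excludes sick sinus syndrome with symptomatic bradycardia and sinus rates below 50 beats per minute, so the patients most prone to the outcome do not enter. Section 1.2 says that "7-day non-invasive Mobile Cardiac Telemetry provided by Preventice will be performed during the two weeks of ScNS to ensure patient safety". Section 4.1 states "Technicians and physicians responsible for echocardiogram and ECG monitoring will be blinded", and section 6.3 that "rhythm analyses performed by the Mobile Cardiac Telemetry system technicians will be blinded". Section 8.3.2 gives symptomatic bradycardia as an example of a serious event. Section 8.3.4 records onset times, so events can be split at crossover afterwards. Adverse events go to the DSMB (8.3.5), whose charter is not in the documents and might call for tables by arm.

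All of this stands, and it limits the point to what the plan says it will tabulate. It does not answer the point: a split made afterwards is not the stated analysis, and the stated rule puts stimulated events under sham.

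A reader might go further and infer that the table could reverse, with sham looking worse on rhythm. With an assumed 5% background and 20% on stimulation, full crossover gives a sham column of 0.05 + 0.95 × 0.20 = 24% against 20%. The documents do not support that as an expectation. Neither risk is theirs, and the active arm is also observed off stimulation after week 2, which the sum ignores. Nor do they support an inference that bradycardia would go unnoticed. An exact count of how many listed outcomes concern rhythm depends on how the list is laid out and adds nothing.

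**Conclusion.** The point holds in limited form. As written, section 9.4.4 mixes sham and stimulated exposure in the sham column once controls cross over, and it has no row for a sinus effect that section 2.3.1 names. The missing cut-off is the more important part, because a stated rule produces a misleading comparison. The missing row is a smaller gap. The absence of an all-event summary by group is mostly missing detail.

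The direction of the dilution follows from the text. Its size rests on the assumed risk on stimulation and the crossover share. Impact is minor to moderate: detection, patient management, the sample size and the primary endpoint at week 1 are unaffected.

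A reader might infer that a baseline-adjusted comparison of sinus rate on the visit ECGs is also required. It is not. Being in sinus rhythm at a visit is a post-randomization state that stimulation is meant to change, so that comparison is a trade-off rather than a correction.

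**What to change.** Change section 9.4.4 in two places.

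1. **Window.** Let the by-group summary cover events from the first implant to the week 3 visit, before any crossover. List later events separately, with those after a second implant in crossed-over controls in a column of their own.
2. **Rows.** Add symptomatic bradycardia of any mechanism, and sinus bradycardia or pause, from the telemetry and ECGs already scheduled. Use a pause of at least 3.0 seconds, as sections 2.3.1 and 7.2 do for asystole; 9.4.4 currently has more than 3.0. The sinus rate that counts is a clinical choice to be stated in advance. Show the adverse and serious adverse events already collected by group over the same window, descriptively.

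The cost is SAP wording and a few table rows. The documents do not say whether the telemetry reports give sinus-rate minima and pauses, so a request to the vendor may be needed.

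Downsides: precision is low (zero events in 15 leaves an upper 95% limit of 1 − 0.025^(1/15) = 21.8%); drug-related bradycardia will appear in both arms; and the investigators who record adverse events know the assignment (section 4.1), so the event tables are open to ascertainment bias and should be read as descriptive.

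### Section 9.4.4 counts sham patients' safety events after crossover under sham, and its list has no row for stimulation-related sensations

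*Combined protocol and SAP*

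**What the plan says.** - **Window.** Section 9.4.4: "Safety shall be evaluated throughout participation in the study".
- **Grouping.** Same section: the number and "percent of patients experiencing a safety outcome listed above will be summarized overall and by randomized group in the safety set".
- **Population.** Section 9.3: "Safety set: the set of patients who have undergone surgery to insert the subcutaneous lead". It has no rule by period or by treatment received.
- **Crossover.** Section 6.1.2: "The control group will have an option to crossover to the experimental group after three weeks from the first procedure". Section 6.3: "This group of patients will undergo a second procedure to receive stimulation at 3.5 mA". Section 2.3.1 adds: "The possibility of a second surgery increases the previous risks".
- **Crossover analysis.** The crossover paragraph in Section 9.4.3 summarizes the characteristics of these patients, and "The averages and SDs of AF burden will be computed for each week from baseline to week 6 for this group". It gives no safety summary.
- **Listed outcomes.** Section 9.4.4 lists major implant events, infection, lead problems, persistent lead-site pain, AV block and bradycardia conditions, skin irritation from patches, and allergic response. Section 2.3.1 also names pain, goosebumps, hot flashes and other discomfort from stimulation as adverse events to be managed medically, and Section 6.3 mentions tingling. Apart from persistent lead-site pain, these have no row.

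**The concern.** Section 4.2 says the arms differ only in output, 3.5 mA against 0 mA. The by-group safety table is therefore the trial's controlled description of harm from stimulation. After crossover, a sham patient has had two implants and two weeks at 3.5 mA, yet stays in the sham column. An infection at the second implant site, or AV block during the active fortnight, would be reported as a sham event.

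The table then no longer compares stimulation with no stimulation. Effects of stimulation appear in both columns, and effects of implantation are counted over more procedures in sham than in Group A. Separately, the discomforts that the protocol itself links to stimulation would mostly not appear in the table.

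**Working it through.** **1. Does any section correct the attribution?** Section 9.4.4 fixes the window (all participation) and the grouping (as randomized). Section 9.3 fixes the population. Sections 6.1.2 and 6.3 put the second implant and the 3.5 mA period inside participation for sham patients who choose it. Section 9.4.3 covers characteristics and AF burden for them. No section stops the safety count at crossover, splits it by period, or gives crossovers a safety table. As written, their later events count under sham.

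**2. Direction of the bias.** Section 9.4.4 states no figure to reproduce, and the documents give no crossover share, so this step is algebra. Let:
- *c* = share of sham patients who cross over;
- *p* = chance of a listed event in one implant period at 3.5 mA;
- *s* = chance of the same event in one implant period at 0 mA.

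Assume that the two periods of a crossed-over patient are independent and that the active period carries the same *p* as in Group A. Events outside these periods are ignored.

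- Group A column: *p*
- Sham column as written: (1 − *c*)*s* + *c*[1 − (1 − *s*)(1 − *p*)] = *s* + *c·p*(1 − *s*)
- Difference shown: (*p* − *s*) − *c·p*(1 − *s*)
- Difference with the count stopped before crossover: *p* − *s*

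The error is *c·p*(1 − *s*). It is zero at *c* = 0 and rises in proportion to *c*. Two special cases:
- *s* = 0 (the event occurs only with stimulation): the difference shown is *p*(1 − *c*). With 15 per arm (Section 9.2) and 5, 10 or 15 crossovers, 1 − 5/15 = 67%, 1 − 10/15 = 33% and 1 − 15/15 = 0% of the true difference remains.
- *c* = 1 and *s* > 0: the difference shown is (*p* − *s*) − *p*(1 − *s*) = −*s*(1 − *p*). This is negative whenever *p* < 1, so sham looks worse even if stimulation is harmful.

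**3. Implant events.** Section 2.3.3 expects 1.2% infection. Section 8.1 gives its source as 1 of 84 patients, and 1/84 = 1.19%, so the figure reproduces. Apply it per implant, with no effect of output:
- Group A patient, one implant: 1.2%
- Crossed-over patient, two implants: 1 − (1 − 0.012)² = 1 − 0.976144 = 2.39%, about 2.4%
- Expected infected patients if all 15 sham patients cross over: Group A 15 × 0.012 = 0.18; sham 15 × 0.0239 = 0.36

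The sham rate doubles with no true difference. In expected counts the gap is 0.18 of a patient.

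**4. Coverage.** Of the sensations in Sections 2.3.1 and 6.3, only pain that is both persistent and at the lead site matches a row. Transient pain, tingling, goosebumps, hot flashes and other discomfort match none.

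**The case against.** The case on the other side is fair on size. The table is descriptive, with no safety test or margin. The overall column is right whichever arm an event is placed in. Section 8.3.4 records onset time, severity and relationship, so a split by period can be made at reporting. The only illustration resting on a protocol rate, infection, moves the expected count by under one-fifth of a patient. All of that stands. It limits the consequence but does not change the stated rule, and choosing the split after seeing the data is weaker than stating it now.

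A second objection is that stopping at week 3 removes later events from the randomized comparison, although Section 2.3.1 lists AV block and infection among its long-range risks and Section 2.3.2 expects that remodeling may persist. This also stands, and is why later events need their own table. Reporting by treatment received or by exposure period would be a valid alternative; what matters is that a rule is stated.

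A reader might infer more than the documents support:
- **That a large, quantified stimulation harm would be hidden.** The plan gives neither a crossover share nor an incidence at 3.5 mA for any listed outcome. Most of the discomforts it names are not in the list at all, so the current table cannot dilute them.
- **That adverse events go unsummarized.** Sections 8.3.5 and 10.1.6 send adverse events and interim data reports to the DSMB, whose charter cannot be seen. One can say only that Section 9.4.4 specifies no table of all adverse events.
- **That unblinding at week 3 is a further bias in the safety assessment.** Section 4.1 says the investigators are never blinded, and Section 6.3 already doubts that patient blinding will hold.
- **That bradycardia, dizziness or syncope are omitted.** The nesting of the bradycardia items cannot be settled from the extracted list, and nothing requires every example of a serious event to be a named endpoint.

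**Conclusion.** The attribution rule is wrong for a trial with optional crossover to active treatment. As written, sham patients' listed events after the second implant and 3.5 mA stimulation count under sham. The by-group table is biased towards no difference, or past it, for stimulation effects, and it inflates the sham column for implant effects.

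The size depends on the crossover share, which is not given: nil if nobody crosses over, and rising in proportion to that share. For infection it is about 2.4% per crossed-over patient against 1.2% in Group A, assuming that 1.2% applies to each implant independently. The direction in step 2 rests on equal risk in the two active periods and on independence between periods.

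The missing row for stimulation sensations is a smaller gap in the same section. Neither problem touches the primary endpoint or loses data.

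**What to change.** In Section 9.4.4:
1. For every listed outcome, make the comparison by randomized group on events from implantation through the week 3 visit in both arms, before any crossover.
2. Tabulate later events separately for Group A, sham without crossover, and sham after crossover. Say where events between the week 3 visit and the second implant go; sham without crossover is the natural place. Keep the overall column.
3. Add one row for stimulation-related sensations (pain, tingling, goosebumps, hot flashes, other discomfort), from the adverse event records already collected.

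A table of all adverse events and serious adverse events would be useful but is optional.

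The cost is a few sentences and some extra descriptive tables, with no new visits or forms. The downside is that events after week 3 leave the randomized comparison and are read from a separate table.
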